#### Introduction

Fatigue is a common symptom reported by people with Parkinson's (PwP) (Herlofson and Kluger 2017). It has significant impact on their quality of life (Herlofson and Kluger 2017; Armstrong and Okun 2020). Patients and clinicians have reported that busy NHS Parkinson's clinics rarely have the time or resource to address this symptom, as they are usually focussing on safety (falls) and mobility issues (Parkinson's UK Audit, 2022). We have conducted a systematic literature review of the efficacy of fatigue management interventions for people with Parkinson's which suggests that CBT and balance-based exercise interventions are the most promising areas to pursue in future research although conclusions are tentative due to the moderate to poor quality and small sample sizes of the available evidence.

We propose that these non-pharmacological interventions may have beneficial effects on fatigue because a wide range of psychosocial and secondary factors contribute to fatigue in Parkinson's including poor sleep, low mood, deconditioning, and unhelpful cognitive behavioural responses to fatigue (Coe et al., 2018).

As both CBT and energy conservation (EC) techniques have evidence of efficacy we are persuaded by the manualised program investigated by Thomas et al (2013) which combined CBT with EC methods for people with multiple sclerosis (MS). The aims of the treatment were to normalise the experience of fatigue, support learning of strategies to manage energy more effectively and to explore different, more helpful ways of thinking about fatigue. Whilst the programme drew upon EC principles the overall aim was not to limit activity but rather to provide individuals with strategies to enable them to do more of the things that matter to them. The program was originally developed for MS so will be adapted to be relevant to people with Parkinson's using input from the lay and clinical advisory groups.

Hebert et al., (2011) propose that balance training in people with MS, may condition central sensory processing for efficient upright postural control, and we propose this may have similar impact in people with Parkinson's. Many patients with Parkinson's, have balance impairments and a high proportion are at risk of falling (Matinolli, M. et al., 2009). Poor balance is likely to make navigating the environment more effortful, and thus a mechanistic

argument can be developed for improvement in balance leading to reductions in fatigue (Cameron & Lord, 2010; Baer, M. et al., 2018). The exercise program will be a recommendation of at least 30 minutes exercise three times a week (in line with the findings of Wu 2020). The exercises will be integrated into the goals of the online ReFresh program. We will ensure that participants have access to a range of online exercise videos from Parkinson's UK of varying intensity. We will also make recommendations for other exercise activities that could be undertaken e.g., walking groups, swimming, dance, Tai Chi etc and provide support to participants on how to integrate exercise as a normal part of their lifestyle. The exact recommendations will be informed by input from the lay and clinical advisory groups.

Finally, this program of fatigue management techniques will be provided in an online format. This will allow people with Parkinson's to independently navigate the program, which allows flexibility in timing and location of the interventions. It removes the need for clinical staff to oversee the intervention, thus reducing its cost and improving its practicality. We recognise that some people with Parkinson's will be excluded because they lack an internet connection, or a computer/ digital phone, or appropriate computer skills to access the website. However, we believe this will be a minority of patients; OFCOM estimates that just 6% of households in the UK remained digitally excluded in regard to internet access in the home (OFCOM 2022). Therefore, we believe this online intervention will be accessible to the majority of potential participants and will provide essential recommendations in an area that is often neglected clinically at the present.

#### Method

#### Design

A pilot randomised controlled trial with **two parallel comparator groups**; the ReFresh online fatigue management program versus a wait list group who will receive treatment as usual, and then access the ReFresh online course at week 14 to ensure all end point data is gathered. We will recommend participants access one **module per week** i.e. six modules over six weeks, and undertake at **least three 30 minute sessions of exercise per week**. The primary outcome will be fatigue at 12 weeks. All measures will be unblinded as it is impossible to blind participants as to whether they have accessed the web site or not.

This pilot study will check study processes (e.g., recruitment, randomisation, treatment, follow-up assessments) all run smoothly, and determine the acceptability and practicality of the ReFresh intervention. It will also appraise the feasibility and sensitivity of two fatigue measures in order to decide which measure will be the primary outcome measure in the fully powered RCT this pilot study will inform. The fatigue measures are the Parkinson's Fatigue Scale (PFS) (Baghoori 2017) and the Modified Fatigue Impact Scale (MFIS) (Fisk et al., 1994). These will be measured at baseline and 12 weeks. Once the primary measure is selected it will inform the number of participants required for a fully powered RCT.

#### Development of the intervention

The development of the intervention will follow the MRC framework for complex interventions (Skivington 2021). The framework divides complex intervention research into four phases: **development or identification** of the intervention, **feasibility**, **evaluation**, and **implementation**. In this case much of the content of a fatigue management intervention has already been developed and just needs refinement for the needs of people with Parkinson's and how to deliver it in an online format. This project will develop (Morely 2004) an online intervention for the management of Parkinson's fatigue blending CBT, EC and exercise promotion that can be accessed outside of existing NHS structures.

The initial assessment of the **feasibility**, and **evaluation** will be conducted in the pilot RCT.

Assessment of the implementation will be independent of the NHS context. Much of the evidence for effective fatigue interventions consist of individual therapy or exercises conducted by a clinicians or therapists. However, in the UK National Health Service (NHS), and elsewhere, clinical resources (both of people and of time) are extremely limited for people with Parkinson's (Parkinson's UK Audit, 2022), thus this approach may prove impractical. Several pilot studies have used online programs which solve the issue of access to therapists, access to transport to the venue the intervention is held at, and a lack of flexibility as to when the intervention is delivered. It is acknowledged that there are other access issues (e.g., lack of access to a computer or the internet) but we believe that overall, the advantages outweigh the disadvantages for most patients.

## Lay and clinical advice

The intervention and RCT design will be informed by three sets of information:

- Evidence from the research literature. Specifically, the systematic review of fatigue management in people with Parkinson's and the scoping review of fatigue management of neurodegenerative conditions.
- 2. Information from lay advisors. Specifically, the panel of six people with Parkinson's will advise on the content of the intervention, design of the RCT, interpretation of the results, and dissemination.
- 3. Information from expert clinicians. Specifically, [name] (independent OT consultant and expert in Parkinson's) and members of the Occupational Therapy for Parkinson's special interest group will advise on the content of the intervention, design of the RCT, interpretation of the results, and dissemination.

The design of the RCT is evidence based, but as the evidence based was sparce in Parkinson's disease, evidence from other neurodegenerative conditions was used to ensure the proposed intervention had sufficient breadth and complexity to address the multifactorial issue of fatigue.

We asked both the clinical and lay advisory teams to examine the proposed ReFresh program. And they have suggested amendments to the draft program to ensure the

proposed intervention matches current best clinical practice, included appropriate safety measures, and was practical for patients to conduct in their own homes..

## Aims

- To determine the size and variance of the difference in change in fatigue between
  the ReFresh group versus the waitlist group at 12 weeks. This will be used calculate
  the number of participants needed to fully power a randomised controlled trial to
  determine efficacy.
- To assess the feasibility, acceptability, and safety, of the ReFresh online fatigue management intervention.
- To assess the feasibility and acceptability of the design of the RCT protocol. In particular to determine which measure of fatigue to use as the primary outcome measure in the planned fully powered RCT.

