#### Randomisation and stratification

Upon completion of baseline data, participants will undergo randomisation to either the intervention arm (fatigue management) or the control arm (waitlist) utilizing the Sealed Envelope website. Sealed Envelope offers a robust online software application for randomising patients into clinical trials and capturing case report form data (EDC and ePRO).

The Simple randomisation service provided by Sealed Envelope will be employed for this trial. This uses a pseudo-randomisation number generator, and will allocate participants in a 1:1 ratio to ReFresh or wait list. To ensure a reasonably even distribution of patients in the 2 arms throughout the course of the trial, patients will be allocated in randomly permuted blocks of 4 and 6 (Sealed Envelope Ltd. 2022).

For the trial, a unique password will be assigned. Authorized personnel with the password will have the capability to conduct new randomisations. The results will be promptly displayed on-screen and emailed to both the trial administrator and the assigned individual overseeing the randomisation process, ensuring transparency and accountability.

Upon allocation participants will be sent an email informing them of their allocation. If allocated to the ReFresh group they will be sent the link to the ReFresh online program https://www.uea.ac.uk/web/groups-and-centres/projects/fatigue-management-in-parkinson-s/refresh-study-getting-started. If they are allocated to the waitlist group they will be told they will be contacted again in 12 weeks to complete the end point survey, and then at 16 weeks with the link to the ReFresh program (to ensure no contamination of the control group).

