## Sample size

The sample size of feasibility and pilot studies is generally influenced by the need to confidently estimate outcome parameters, such as standard deviation, for use in the sample size calculation of a definitive trial. According to Lancaster, Dodd, and Williamson (2004), a sample size of 30 is often considered a good rule of thumb.

We will adhere to this guideline by recruiting 20 participants for each arm of the study, resulting in a total of 40 participants. This sample size will allow us to collect sufficient data to estimate outcome parameters effectively and inform the design of future definitive trials.

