#### **Efficacy Analyses**

As this is a pilot RCT an accurate assessment of the efficacy of the intervention cannot be determined as the study is insufficiently powered. However, we will analyse the primary outcome measure at 12 weeks using the parametric student-t test for comparing mean change between the two intervention groups.

Intention to Treat (ITT) analyses will be performed for all outcomes and will comprise of all patients who had been randomised. For the intervention group, this was irrespective of their compliance with the ReFresh program. The principle of ITT was adopted as it provides a pragmatic estimate of the benefit of a change in treatment policy compared to the potential benefit in patients who receive treatment exactly as planned. As the ReFresh program was planned for delivery over a six-week period, some participants may not have received all the planned sessions. As this is more likely to reflect usual practice, primary analyses of all outcomes were conducted according to the ITT principle. Per Protocol (PP) analyses was planned for participants who had not deviated from the ReFresh protocol in such a manner that the assessment of efficacy could be biased. This was defined as patients accessing at least four out of six ReFresh modules. Imputation of missing/incomplete data is planned to use last observation carried forward method for all outcome measures.

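### Aim 1 sizes the definitive trial on the treatment difference observed in 40 people, which the pilot can estimate only to about ±0.64 SD of change

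*Protocol*

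**What the plan says.** The first item under Aims is "To determine the size and variance of the difference in change in fatigue between" the ReFresh and waitlist groups at 12 weeks. The next sentence gives its purpose, which is to calculate "the number of participants needed to fully power a randomised controlled trial to" determine efficacy. Both the observed difference and its variance are therefore inputs to the next trial's sample size.

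Two other sections bear on this:
- Sample size bases the number on "the need to confidently estimate outcome parameters, such as standard deviation", cites a conventional figure of 30, and settles on "recruiting 20 participants for each arm of the study, resulting in a total of 40 participants". It concludes: "This sample size will allow us to collect sufficient data to estimate outcome parameters effectively".
- Efficacy Analyses concedes that "an accurate assessment of the efficacy of the intervention cannot be determined as the study is insufficiently powered", and plans a "parametric student-t test for comparing mean change between the two intervention groups".

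The protocol gives no target or minimally important difference for the MFIS or the PFS. It also gives no significance level or power for the definitive trial.

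**The concern.** The protocol says that efficacy cannot be accurately assessed in this study, yet its first aim feeds the observed efficacy estimate into the planning of the next one. The Sample size section offers no support for that use, because the only parameter it names is the standard deviation.

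The required sample size varies with the inverse square of the assumed difference, so error in the pilot difference is magnified. A difference that is high by chance yields a definitive trial that is too small to detect the true effect. One that is low by chance yields a trial far larger than needed. A zero or negative one yields no usable sample size.

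**Working it through.** **Inputs from the protocol.** There are 20 per arm (Sample size); randomisation "will allocate participants in a 1:1 ratio to ReFresh or wait list" (Randomisation and stratification); and the analysis is a two-sample t-test on mean change (Efficacy Analyses), so 38 degrees of freedom if all 40 contribute. No SD is given, so everything is in units of the SD of change.

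**Assumptions, because the protocol gives no figures.** Two-sided 5% and 90% power for the definitive trial; a true effect of 0.4 SD, with 0.3 and 0.5 as a range; no dropout; and the raw pilot estimate plugged in.

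**1. The plan's own figure.** 2 × 20 = 40 is consistent. It rests on a convention, so there is no power or precision calculation to reproduce.

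**2. Precision of the difference.** Half-width = t(0.975, 38) × √(2/20) = 2.024 × 0.316 = 0.640 SD. With 15 completers per arm it would be 0.75 SD.

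**3. One pilot as an example.** n per arm = 2 × (1.960 + 1.282)² / d². At d = 0.4 this is 131.3 (132 when rounded up). An observed 0.4 SD has a 95% interval of −0.24 to 1.04 SD. The upper limit gives 20 per arm, and the lower limit gives no sample size at all.

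**4. Long-run behaviour.** If n is set from the observed standardised difference g, the definitive trial's true power is Φ(3.242 × d/g − 1.960). With d = 0.4 and a standard error of 0.316, ignoring error in the SD:
- Power is below 80% when g > (3.242/2.802) × 0.4 = 0.463. The probability is P(Z > 0.063/0.316 = 0.20) ≈ 0.42.
- Power is below 50% when g > (3.242/1.960) × 0.4 = 0.662. The probability is P(Z > 0.262/0.316 = 0.83) ≈ 0.20.
- The difference is zero or negative with probability Φ(−0.4/0.316) ≈ 0.10.

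Simulation of 200,000 pilots per true effect, with the SD also estimated, agrees:

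| True effect (SD) | Definitive trial below 80% power, share of all pilots | Zero or negative difference, share of all pilots | Calculated n within a factor of 2 of the correct n, share of all pilots |
|---|---|---|---|
| 0.3 | 44% | 17% | 26% |
| 0.4 | 43% | 10% | 34% |
| 0.5 | 41% | 6% | 41% |

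At 0.4 SD, about 21% of all pilots lead to true power below 50%. Among pilots with a positive difference only, the middle half of the calculated sizes runs from about 50 to 309 per arm, against 131 needed. The first two percentage columns do not overlap: pilots with a zero or negative difference are not counted among those below 80% power.

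**5. What the pilot does estimate usefully.** The 95% limits for the SD, √(38/χ²), are 0.82 and 1.29 times the estimate, so n varies by a factor of 0.67 to 1.66. The one-sided 80% upper limit is 1.12 times the estimate. If the target difference is fixed in advance and equals the true effect, the share of pilots leading to power below 80% falls from about 43% to about 13% using the estimated SD, and to about 2.4% using that upper limit.

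**The case against.** The best defence is that this is a pilot, that its authors acknowledge the limits, and that nothing in recruitment, allocation, measurement or the 12-week analysis depends on the point. The definitive trial will have its own protocol, with its own target difference, alpha and power. Aim 1 gives no formula, so plugging in the raw estimate is one reading; a later team could add outside evidence or shrink the estimate.

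Much of that stands, and it limits the severity. It does not remove the fault: Aim 1 names the size of the difference as an input, no other section withdraws it, and no alternative target is given. A separate analysis plan that dropped this use would contradict the aim.

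A reader might infer three stronger things that the protocol does not support:
- *That this is the main decision the pilot informs, or that a low result would end the programme.* Aims lists three purposes, and Design puts study processes, acceptability and choice of measure ahead of sample size. There is no stop/go rule tied to the observed difference.
- *That the Sample size section claims 40 people estimate the effect well.* It speaks of outcome parameters in general and names only the standard deviation.
- *That 40 is too few for a pilot.* The same 40 serve adequately for the SD. The fault is in the use made of the result.

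**Conclusion.** The concern holds, confined to the word size in Aim 1. The half-width of 0.64 SD follows from the protocol's own numbers and is a best case, since it allows for no dropout. The long-run percentages rest on the assumed alpha, power, effect sizes and plug-in rule. They change little across true effects of 0.3 to 0.5 SD, where 41% to 44% of all pilots lead to a definitive trial below 80% power. The aim also conflicts with the concession under Efficacy Analyses. It should be corrected, but it is not a condition for running the pilot: the data would be the same, and only what they may be used to conclude changes.

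**What to change.** Reword Aim 1 and the Sample size section as follows.
- The pilot supplies the SD of change, the baseline correlation and retention. For the SD, preferably use a stated upper confidence limit; the one-sided 80% limit, about 1.12 times the estimate, is one reasonable convention among several.
- The definitive trial is powered for a minimally important difference, stated and justified for both the MFIS and the PFS before the pilot data are analysed. Both are needed because the primary scale is itself to be chosen from those data.
- The observed difference is reported with its 95% confidence interval, only to check whether the important difference remains plausible.

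The cost is the work of justifying a difference on two scales, plus a somewhat larger planned definitive sample: using the upper SD limit multiplies n by 1.116² ≈ 1.25. The pilot needs no additional participants, visits or measures.

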## **RCT Registration**

The RCT will be registered with ISRCTN.

## **Participants**

#### Inclusion criteria

- People with a clinical diagnosis of idiopathic Parkinson's disease
- Any co-morbidity except those in the exclusion criteria
- Ambulatory
- Aged 18 years and over.
- Living in England
- Are English speaking and literate.
- Have access to the internet.
- Have the ability to complete online assessments. (Competency to consent will be assumed by the ability to complete the online surveys).

#### **Exclusion criteria**

- Any diagnoses of other Parkinsonian conditions e.g., vascular Parkinsonism,
   progressive supranuclear palsy, multiple system atrophy, Lewy body dementia
- Anyone who has been clinically recommended to not undertake exercise.

#### **Recruitment Strategy**

Participants will be recruited from Parkinson's UK using their newsletter and their Research Support Network (RSN). The RSN has over 5000 members. We will also recruit using adverts with the Cure Parkinson's charity and relevant social media groups. We have previously recruited using this method to a two-stage survey on anxiety with 205 and 341 participants recruited over 2 and 4 months respectively, and to a survey on medication adherence with 790 participants recruited over 6 months. Therefore, we believe recruiting 40 participants over 2 months is realistic. We will track the route participants took to be recruited to the study in order to identify the most effective recruitment strategies.

The participants will be directed to the project's web site:

https://www.uea.ac.uk/web/groups-and-centres/projects/fatigue-management-in-parkinson-s

There they will be provided with information on the study and invited to follow a link to a survey hosted on the Qualtrics system to complete their consent and baseline assessments: https://qualtricsxm3xhpzbjcj.qualtrics.com/jfe/form/SV\_bKJmAZXD5lTE43I . Qualtrics is reasonably accessible (i.e. works with most screen readers) and is UK GDPR compliant.

#### Randomisation and stratification

Upon completion of baseline data, participants will undergo randomisation to either the intervention arm (fatigue management) or the control arm (waitlist) utilizing the Sealed Envelope website. Sealed Envelope offers a robust online software application for randomising patients into clinical trials and capturing case report form data (EDC and ePRO).

The Simple randomisation service provided by Sealed Envelope will be employed for this trial. This uses a pseudo-randomisation number generator, and will allocate participants in a 1:1 ratio to ReFresh or wait list. To ensure a reasonably even distribution of patients in the 2 arms throughout the course of the trial, patients will be allocated in randomly permuted blocks of 4 and 6 (Sealed Envelope Ltd. 2022).

For the trial, a unique password will be assigned. Authorized personnel with the password will have the capability to conduct new randomisations. The results will be promptly displayed on-screen and emailed to both the trial administrator and the assigned individual overseeing the randomisation process, ensuring transparency and accountability.

Upon allocation participants will be sent an email informing them of their allocation. If allocated to the ReFresh group they will be sent the link to the ReFresh online program https://www.uea.ac.uk/web/groups-and-centres/projects/fatigue-management-in-parkinson-s/refresh-study-getting-started. If they are allocated to the waitlist group they will be told they will be contacted again in 12 weeks to complete the end point survey, and then at 16 weeks with the link to the ReFresh program (to ensure no contamination of the control group).

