## Blinding

Blinding to group allocation will not be possible as participants will know whether they had access to the online fatigue management program. All assessments will be completed by participants via online surveys. The trial data will be analysed by SA who will not be blinded to allocation.

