## Data security

Only members of the research group (members are listed at the start of this protocol) will have access to the data during the project.

Most of the assessments and consent will be recorded online using the Qualtric survey platform. However, to ensure accessibility for participants with disability access needs, participants will be offered hard copy survey and consent forms to be posted to them (including a postage paid return envelope). If participants take up this option, the information on these hard copies will be transcribed by SA into the Qualtrics surveys. All hard copy surveys and consent forms will be destroyed as soon as the data is transcribed to the Qualtrics platform.

The data will be downloaded from the Qualtrics platform to the secure UEA server, and the original data will be deleted from the Qualtrics platform by September 31st, 2025. The contact details will be kept only until everyone involved in the trial has been sent a link to the online fatigue management intervention i.e., 14 weeks after randomisation (September 31st, 2024, latest). After this we will destroy the contact details and keep the anonymised dataset of results.

Project data will be deleted from the UEA shared drive 10 years after the end of the project (i.e., 31st September 2035). Only anonymised data will be shared externally (e.g., in reports and publications).

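### The protocol publishes the block sizes (4 and 6) of one open, unstratified list and sets no explicit randomisation order, leaving a possible but probably small route to selection

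*Protocol*

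**What the plan says.** The protocol's section on randomisation and stratification describes the procedure as follows.

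- Timing: "Upon completion of baseline data, participants will undergo randomisation".
- System: "The Simple randomisation service provided by Sealed Envelope will be employed for this trial". The service "will allocate participants in a 1:1 ratio to ReFresh or wait list", and "patients will be allocated in randomly permuted blocks of 4 and 6". Despite the section title, no stratification factor is named, so there is a single list.
- Who starts it: "Authorized personnel with the password will have the capability to conduct new randomisations".
- Who sees the results: "The results will be promptly displayed on-screen and emailed to both the trial administrator and the assigned individual overseeing the randomisation process".

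The Data security section offers posted paper forms as an alternative to the online survey and says that "the information on these hard copies will be transcribed by SA into the Qualtrics surveys". The Blinding section makes the trial open. The Sample size section sets 20 participants per arm, 40 in total.

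The protocol does not say that the block sizes are withheld from those who randomise. It gives no explicit rule for the order in which people with a completed baseline enter the list.

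**The concern.** A central web service hides the list itself. It does not stop the next allocation being inferred by someone who knows the block sizes and has seen the earlier allocations. Here the sizes are printed, the trial is open, and those who start each randomisation see the results. Baseline fatigue scores exist before allocation.

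If two or more people are waiting, or a paper form is waiting to be keyed, the order in which they enter could be influenced by the expected next arm. The arms could then differ by selection rather than chance. At stake is the first aim: the size and variance of the between-arm difference in change in fatigue, from which the full trial will be sized. The pilot is also meant to test the randomisation process, so a weak procedure could carry over into the full trial.

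**Working it through.** The protocol gives no predictability figure, so there is none to reproduce.

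**Inputs.** Block sizes 4 and 6, ratio 1:1, one list and visible past allocations (randomisation section); N = 40 (Sample size). *Assumption:* each block is 4 or 6 with probability 0.5, independently. The observer knows the sizes and the full history, but not where blocks begin and end.

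**One case by hand.** Suppose the first two allocations are to the same arm.
- Probability of this (for a given arm) in a block of 4: 2/4 × 1/3 = 1/6. In a block of 6: 3/6 × 2/5 = 1/5.
- Posterior probability that the block has size 4: (1/6) / (1/6 + 1/5) = 0.455.
- Probability that the third goes to the other arm: 0.455 × 1 + 0.545 × 0.75 = 0.864.

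**Whole sequence.** The same updating was applied to 30,000 simulated lists of 40.
- Predictable with at least 80% probability: 27.6%, or 11.05 of 40 (5th to 95th percentile 5 to 17). Such guesses are right 89% of the time.
- Predictable with certainty: 5.6%.
- Best guess correct: 69% (in an 8,000-list run), against 50% if allocations were unpredictable.

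**Sensitivity to the mix.** Share predictable with at least 80% probability, by the probability of size 4:
- 0.2: 25.2%
- 0.3: 27.4%
- 0.4: 35.3%
- 0.45: 28.5%
- 0.5: 27.6%
- 0.55: 24.6%
- 0.6: 26.2%
- 0.7: 32.2%
- 0.8: 35.1%

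Four blocks of each size in random order give 31.7%. The jumps come from the fixed 80% cut-off. For an observer who also knew each block's size, exact enumeration gives certainty for 33.3% of a block of 4 and 25.0% of a block of 6. Pooled, this is (4 × 33.3 + 6 × 25.0)/10 = 28.3%.

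**A simpler observer.** Guess whichever arm is behind. In simulation the running difference is 0, 1, 2 or 3 before 39%, 49%, 11% and 1% of assignments. The lagging arm comes next with probability 0.784, 0.912 and 1 at differences of 1, 2 and 3. Overall accuracy is 0.39 × 0.5 + 0.49 × 0.784 + 0.11 × 0.912 + 0.01 × 1 = 0.69. So 69% accuracy needs only the history, not the sizes.

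**Possible effect on the estimate (illustrative).** Let the person randomising shift the chosen participant's baseline score by d SD according to the guess.
- Baseline imbalance = 2d(2p − 1). With p = 0.689 this is 0.76d.
- With d = 0.25 (assumed): 0.19 SD if discretion applies to everyone, and 0.19/4 = about 0.05 SD if it applies to a quarter of participants.
- Effect on the change score = imbalance × (1 − r), where r is the baseline to 12-week correlation and variances are equal. With r from 0.5 to 0.8 (assumed): 0.095 to 0.04 SD in the first case, and 0.025 to 0.01 SD in the second.
- Standard error of the change difference = √(2(1 − r)) × √(1/20 + 1/20) = 0.32 SD at r = 0.5 and 0.20 SD at r = 0.8. The larger effect is 0.095/0.32 = 0.30 and 0.04/0.20 = 0.20 of a standard error, so below a third.

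**Other sizes.** With 4, 6, 8 and 10 known to the observer, 14% are predictable with at least 80% probability and 1.3% with certainty; the best guess is right 66% to 67% of the time. The mean difference in arm sizes rises from 0.45 to about 0.65 to 0.70 participants.

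**The case against.** The strongest case against the point is that the protocol leaves little to exploit. Randomisation is tied to completion of baseline, which most naturally means each person in turn. Participants refer themselves, consent and complete measures online, and no staff screening step is described. Forty people over two months is less than one a day, so a queue may be rare. The list is concealed centrally and the block sizes are mixed. The 28% figure needs an assumed mix and an observer who does a careful calculation, and it falls just below a quarter at one mix.

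Much of this stands, and it limits the point. Three stronger readings are tempting but not supported.

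- *Staff can choose who is randomised next.* A reader might infer this because no order is set. The protocol does not say it, and the wording on timing points towards completion order.
- *Nothing later would correct an imbalance.* The efficacy analysis compares mean change, which removes part of an imbalance in baseline fatigue. It does not remove an imbalance in factors that are not measured.
- *One person controls both entry and allocation.* The team member who keys paper forms also analyses the data unblinded, but the protocol does not say that this person holds the randomisation password. Unblinded analysis has no bearing on allocation concealment, and the number of paper forms is unknown.

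What remains is that completion order is implied rather than required. Newsletter and social media recruitment can bring people in bursts; the protocol reports 205 survey participants in two months by the same route. The date on which a paper baseline becomes complete depends on when it is keyed. The need for a careful calculation is also only a partial answer, since guessing the lagging arm gives the same 69%.

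**Conclusion.** The point holds as a weakness in the concealment procedure, not as evidence of bias. With equally likely block sizes, about 28% of the 40 assignments can be predicted with at least 80% probability, about 6% with certainty, and 69% are guessed correctly. The first figure ranges from about 25% to 35% over the other mixes tried, and all three assume an observer with the full allocation history.

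The room to use that knowledge is limited to the order or timing of people whose baseline is complete or waiting to be keyed. Any effect on the fatigue estimate is probably small: in the illustration it stays below a third of a standard error even if discretion applied to every participant. That illustration rests on assumed values for d and r and covers only selection on baseline fatigue. It is worth correcting because the remedy costs almost nothing and the procedure may be reused in the full trial.

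**What to change.** 1. Add an order rule to the randomisation section: *Participants are randomised strictly in order of baseline completion, by Qualtrics submission time stamp or, for paper forms, by date of receipt; a paper form is keyed before any later submission is randomised.*
2. Remove the block sizes from the protocol and state: *Block sizes vary, are set in the randomisation service by a person not involved in enrolment, data entry or analysis, and are not disclosed to the study team.* The printed sizes are already known, so new ones are needed, for example 4, 6, 8 and 10.

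The order rule is the main protection, because it removes the discretion whatever can be guessed. New sizes mainly reduce the near-certain predictions; if they became known, best-guess accuracy would fall only from 69% to about 66% to 67%.

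The cost is two sentences, one changed setting and a colleague's time once. Final balance is slightly looser, with a mean arm-size difference of about 0.65 to 0.70 instead of 0.45 participants. No extra participants or procedures are needed.
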